#### 15.3.1. Definitions of Assessment Windows for Analyses

Analysis Time Point	Definitions
Screening 	Data collected in Screening visit If multiple records are present, the latest record will be used for analysis.
Day 1 	Data collected in Day 1 visit If multiple records are present, the latest record will be used for analysis.
Week 2	Data collected in Week 2 visit
Week 4	Data collected in Week 4 visit
Week 6	Data collected in Week 6 visit
...	...
Week 48	Data collected in Week 48 visit
Week 50	Data collected in Week 50 visit
Week 52	Data collected in Week 52 visit
Follow-up	Data collected in Follow-up visit

**Note:**

Any unscheduled visit will not be slotted to a particular time point.

[1] For rescreened subjects, data collected in screening-pass visit (i.e., screening and day 1 visit where the subject has passed a screening test) will be used for analysis. They may have multiple records at Screening and/or Day 1 visit, which associates with a screening pass visit and screening failure visit(s) (See Section [15.6.1](#))

## 15.4. Appendix 4: Study Phases and Treatment Emergent Adverse Events

### 15.4.1. Study Phases

Assessments and events will be classified according to the time of occurrence relative to randomization date and treatment stop date.

Treatment stop date is defined in Section 15.6.1.

#### 15.4.1.1. Study Phases for Hgb Data

Treatment State	Definition
Pre-therapy	Date ≤ Randomization Date
On-therapy	Randomization Date < Date ≤ Treatment Stop Date + 1 day
Post-therapy	Date > Treatment Stop Date + 1 day

**NOTES:**

- If randomization date is missing then the assessment will be considered to be pre-therapy

#### 15.4.1.2. Study Phases for AE Data

On-therapy AEs will be treated as treatment emergent AEs, therefore, treatment emergent flag for AEs will be derived from on-therapy treatment state.

Treatment State	Definition
Pre-therapy	AE Start Date < Randomization Date
On-therapy	Randomization Date ≤ AE Start Date ≤ Treatment Stop Date + 1 day
Post-therapy	AE Start Date > Treatment Stop Date + 1 day
Duration (Days)	AE Resolution Date – AE Onset Date + 1 day
Drug-related	If relationship is marked 'YES' on eCRF or value is missing.

**NOTES:**

- If randomization date is missing then the assessment will be considered to be pre-therapy

#### 15.4.1.3. Study Phases for Concomitant Medication

Treatment State	Definition
Pre-therapy	Concomitant medications that meet either following conditions will be regarded as pre-therapy. 
 
• Concomitant Medication Start Date < Randomization Date [a, b, c, j, n]
 
• Concomitant Medication Start Date is missing [g, h, i, m, o]
 
• Randomization Date is missing
 

On-therapy	Concomitant medications that meet either following conditions will be regarded as on-therapy. 
 
• Randomization Date ≤ Concomitant Medication Start Date ≤ Treatment Stop Date + 1 [d, e, k, p, q, r, s, v]
 
• (Concomitant Medication Start Date < Randomization Date) AND (Randomization Date ≤ Concomitant Medication Stop Date) [b, c, n]
 

Treatment State	Definition
	
 
(Concomitant Medication Start Date < Randomization Date) AND (Concomitant Medication Stop Date is missing) [j]
 
(Concomitant Medication Start Date is missing) AND (Concomitant Medication Stop Date ≥ Randomization Date) [h, i, o]
 
(Concomitant Medication Start Date is missing) AND (Concomitant Medication Stop Date is missing) [m]
 

Post-therapy	Concomitant medications that meet either following conditions will be regarded as post-therapy. 
 
Concomitant Medication Stop Date > Treatment Stop Date [c, e, f, l, r, t, v]
 
Concomitant Medication Stop Date is missing [j, k, l, m, s, u]
 

**NOTES:**

- Data of concomitant medication includes ESA, iron, and blood products and blood supportive care products.
- Alphabets in brackets after the conditions correspond to each case in following illustrations.

Illustrations of the pre-therapy, on-therapy, and post-therapy for concomitant medications are included below:

	Pre-therapy	On-therapy		Post-therapy	Pre-therapy medication	On-therapy medication	Post-therapy medication
(a)	x—x				Y	N	N
(b)	x—		—x		Y	Y	N
(c)	x—		—	—x	Y	Y	Y
(d)		Randomization Date	x—x		N	Y	N
(e)			x—		N	Y	Y
(f)				Treatment Stop Date	N	N	Y
(g)	?—x			Treatment Stop Date + 1 Days	Y	N	N
(h)	?—		—x		Y*	Y	N
(i)	?—		—		Y*	Y*	Y
(j)	x—		—		Y	Y**	Y**
(k)			x—		N	Y	Y**
(l)					N	N	Y
(m)	?—		—		Y***	Y***	Y***
(n)	x—	x			Y	Y	N
(o)	?—	x			Y*	Y	N
(p)		x	—x		N	Y	N
(q)		x	—	x	N	Y	N
(r)				x	N	Y	Y
(s)				x	N	Y	Y**
(t)				x	N	N	Y
(u)				x	N	N	Y
(v)			x—	x	N	Y	Y

x = start/stop date of medication  
 ? = missing start/stop date of medication  
 \* If a medication is stopped on-therapy or post-therapy and no start date is recorded it will be assumed that the medication was ongoing from the pre-therapy phase  
 \*\* If a medication is started pre-therapy or on-therapy and no stop date is recorded then usage will be assumed to be ongoing for the remainder of the study  
 \*\*\* If a medication has no start or stop date it will be assumed that the medication was ongoing from the pre-therapy phase to the post-therapy phase

## 15.5. Appendix 5: Data Display Standards & Handling Conventions

### 15.5.1. Reporting Process

Software	

 
The currently supported versions of SAS software and S-Plus will be used.
 
	
Reporting Area	
HARP Server	: uk1salx00175
HARP Compound	: /arenv/arprod/gsk1278863/mid201754/final_01
QC Spreadsheet	: /arenv/arprod/gsk1278863/mid201754/final_01/documents
Analysis Datasets	

 
Analysis datasets will be created according to CDISC standards (SDTM IG Version 3.1.3 & ADaM IG Version 1.0. If the Study Data Standardization Plan (SDSP) exists for a study, ensure the CDISC versions are consistent.
 
	
Generation of RTF Files	

 
RTF files will not be generated.
 
	

### 15.5.2. Reporting Standards

General	

 
The current GSK Integrated Data Standards Library (IDSL) will be applied for reporting, unless otherwise stated (IDSL Standards Location: https://spope.gsk.com/sites/IDSLLibrary/SitePages/Home.aspx):             
 
4.03 to 4.23: General Principles
 
5.01 to 5.08: Principles Related to Data Listings
 
6.01 to 6.11: Principles Related to Summary Tables
 
7.01 to 7.13: Principles Related to Graphics
 
 
 
Do not include subject level listings in the main body of the GSK Clinical Study Report. All subject level listings should locate in the modular appendices as ICH or non-ICH listings
 
	
Formats	

 
GSK IDSL Statistical Principles (5.03 & 6.06.3) for decimal places (DP's) will be adopted for reporting of data based on the raw data collected, unless otherwise stated.
 
Numeric data will be reported at the precision collected on the eCRF.
 
The reported precision from non eCRF sources will follow the IDSL statistical principles but may be adjusted to a clinically interpretable number of DP's.
 
	
Planned and Actual Time	

 
Reporting for tables, figures and formal statistical analyses:             
 
Planned time relative to dosing will be used in figures, summaries, statistical analyses and calculation of any derived parameters, unless otherwise stated.
 
The impact of any major deviation from the planned assessment times and/or scheduled visit days on the analyses and interpretation of the results will be assessed as appropriate.
 
Scheduled visits outside the protocol defined time-windows (i.e. recorded as protocol deviations) will be included in listings, figures, summaries and statistical analyses.
 
 
 
Reporting for Data Listings:             
 
Planned and actual time relative to study drug dosing will be shown in listings (Refer to IDSL Statistical Principle 5.05.1).
 
Unscheduled or unplanned readings will be presented within the subject's listings.
 
 
 
	

Unscheduled Visits	

 
Unscheduled visits will not be included in summary tables and/or figures. 
 
If unscheduled visits are included, details of how summaries will be displayed will be provided in the RAP.
 
 
 
All unscheduled visits will be included in listings.
 
	
Descriptive Summary Statistics	
Continuous Data	Refer to IDSL Statistical Principle 6.06.1: This does not apply to the output of statistical models or when the standard list is inappropriate. 
 
For cases where the standard may not be applied, see the display details in Section 6 to Section 10.
 

Categorical Data	N, n, frequency, %
Graphical Displays	

 
Refer to IDSL Statistical Principals 7.01 to 7.13.
 
	

### 15.5.3. Reporting Standards for Pharmacokinetic

Pharmacokinetic Concentration Data	
PC Windows Non-Linear (WNL) File	PC WNL file (CSV format) for the non-compartmental analysis by Clinical Pharmacology Modelling and Simulation function will be created according to GUI_51487. Note: Concentration values will be imputed as per GUI_51487
Descriptive Summary Statistics, Graphical Displays and Listings	Refer to IDSL PK Display Standards. Refer to IDSL Statistical Principle 6.06.1. Note: Concentration values will be imputed as per GUI_51487 for descriptive summary statistics/analysis and summarized graphical displays only.
Pharmacokinetic Parameter Derivation	
PK Parameter to be Derived by Programmer	The following PK parameters will be derived by the Programmer: 
 
Dose-Normalized PK parameters
 

Pharmacokinetic Parameter Data	
Is NQ impacted PK Parameters Rule Being Followed	Yes, refer to Standards for Handling NQ Impacted PK Parameters.
Descriptive Summary Statistics, Graphical Displays and Listings	Each pharmacokinetic parameter (AUC(0-4), C max , and T max ) will be summarized using the minimum set of summary statistics (IDSL statistical display principle 6.06.1). For each pharmacokinetic parameter (AUC(0-4), C max , and T max ), the log-transformed parameter will be summarized using the summary statistics. The summary statistics are: N, n, geometric mean, 95% CI of geometric mean, standard deviation (SD) of log-transformed data and between subject coefficient of variation (CV b (%)) will be reported. [1] $CV_b (\%) = \sqrt{(\exp(SD^2) - 1) * 100}$ (SD = SD of log transformed data)

## 15.6. Appendix 6: Derived and Transformed Data

### 15.6.1. General

Multiple Measurements at One Analysis Time Point

 
Subjects having both High and Low values for Normal Ranges at any post-baseline visit for safety parameters will be counted in both the High and Low categories of “Any visit post-baseline” row of related summary tables. This will also be applicable to relevant PCI summary tables.
 
For multiple measurements at Screening and/or Day 1 visit, the screening-pass visit record will be used for analysis (See Appendix 3).
 

Study Day

 
Calculated as the number of days from Randomization Date:             
 
Ref Date = Missing → Study Day = Missing
 
Ref Date < Randomization Date → Study Day = Ref Date – Randomization Date
 
Ref Date ≥ Randomization Date → Study Day = Ref Date – (Randomization Date) + 1
 
 
 

Unique Subject ID

 
All subjects have unique subject ID for analyses even if a subject was enrolled after rescreened. Tables/figures/listings will be produced based on unique subject ID.
 
For a rescreened subject, the unique subject ID will be derived from the first-assigned subject number though he or she seems to have different subject numbers in eCRF by screening assessments.
 

Rescreening Subjects

 
For rescreened subjects, data collected in screening-pass visit will be used for analysis. They may have multiple records at Screening and/or Day 1 visit, which associates with a screening-pass visit and screening failure visit(s)
 
Regarding a listing of SAEs in screening period, all pre-therapy SAEs captured in eCRF will be provided including screen failure records of rescreened subjects.
 

Treatment Start Date

 
First randomized treatment start date
 

Treatment Stop Date - Daprodustat

 
Calculated as the latest randomized treatment stop date
 

Treatment Stop Date – Darbepoetin Alfa

 
Following definition will be based on “assumed” treatment stop date because the treatment stop date is not captured in eCRF.
 
 
Definition:
 
 
If a subject has completed the treatment period (i.e., Week 52 visit record is present), treatment stop date will be calculated as Week 52 visit date             
 
Week 52 visit date will be based on laboratory Hgb date. HemoCue Hgb date will be used when laboratory Hgb date is unavailable.
 
 
 
If a subject has withdrawn from the treatment period (i.e., Week 52 visit record is missing), treatment stop date will be calculated as the latest treatment start date + 6 days (1 day before the next treatment start date if a subject hadn’t withdrawn)             
 
Subjects are intended to have weekly injection of darbepoetin alfa, therefore assumed treatment stop date could include “+ 6 days” to mimic weekly dosing.
 
 
 

Subgroup Definition

 
For general considerations, see Section 5.4.2.
 
Regarding prior ESA type and prior ESA dose, see Section 15.6.2
 
Period of time on dialysis (years) will be defined as follows:                         
 
(Randomization Date – Date of Dialysis Initiation + 1) / 365.25
 
 
 
Baseline iron use = use or non-use of pre-therapy iron medications (including Riona and P-TOL, see Section 15.6.6)
 
History of diabetes will be derived from the current history diabetes (Yes/No) in medical history records.
 

Time Definitions (per GSK standard principles)

 
1 week = 7 days
 
1 month = 30.4375 days
 
1 year = 365.25 days
 

### 15.6.2. Study Population

Subject Disposition and Study Population
Rescreened Subjects

 
Screening status and reason for screening failure for a subject who has multiple subject numbers will be unique in the unique subject ID.                         
 
The screening status of a subject who failed screening but passed rescreening will be ‘enrolled’, and the reason for failure will not be counted.
 
The screening status of a subject who failed more than one screening and never passed will be ‘failed’, and the reason for failure will be derived from the latest failure record.
 
 
 
Study population of subjects will be derived from the above unique screening status.
 

Demographics and Baseline Characteristics										
Age										

 
GSK standard IDSL algorithms will be used for calculating age where birth date will be imputed as follows:                         
 
A date and month will be imputed as ‘30th June’ as it will not be captured.
 
 
 
Randomization date will be used as reference date of calculation.                         
 
If randomization date is missing, screening date will be used.
 
 
 
										
Body Mass Index (BMI)										

 
Calculated as Weight (kg) / [Height (m)]
 
										
Type of Prior ESA										

 
For this study, prior ESA dose can be administered in several different ways, which are categorized by GSK drug codes as follows.
 
 
  
 Prior ESA	Epoetin	Epoetin beta pegol	Darbepoetin alfa	
   
 CMDRGCOL	00928302	53876201	50520401	
 
 00928303	
 
 00928305	
  
 
 
Dosing route (IV or SC) will be derived from eCRF.
 
	Prior ESA	Epoetin	Epoetin beta pegol	Darbepoetin alfa	CMDRGCOL	00928302	53876201	50520401	00928303	00928305
Prior ESA	Epoetin	Epoetin beta pegol	Darbepoetin alfa							
CMDRGCOL	00928302	53876201	50520401							
	00928303									
	00928305									
Prior ESA Dose (IU/week) at Baseline										

 
During screening, subjects may be receiving ESA in multiple ways, including epoetin IV or SC, darbepoetin alfa IV or SC, or epoetin beta pegol IV or SC. The dose of ESA at screening visit will be
 
										

### Demographics and Baseline Characteristics

standardized to obtain a continuous single unit prior ESA dose in terms of epoetin IV (IU/week). The standardization will be carried with the following formula based on literature review:

- For subjects taking epoetin IV
  - Standardized mean prior ESA dose (IU/week) = epoetin IV dose (IU/week)
- For subjects taking epoetin SC
  - Standardized mean prior ESA dose (IU/week) = (161/113)\*epoetin SC dose(IU/week): [Besarab. 2002]
- For subjects taking darbepoetin alfa IV or SC
  - Standardized mean prior ESA dose (IU/week) = 250\*darbepoetin alfa dose (µg/week)
- For subjects taking epoetin beta pegol IV or SC
  - Standardized mean prior ESA dose (IU/week) = 208\*epoetin beta pegol dose (µg/week)
- Prior ESA dose will be calculated using a weighted mean:
  - Mean prior ESA dose (µg/week or IU/week) =  $([dose\_w]_1 * [duration]_1 + \dots + [dose\_w]_n * [duration]_n) / ([duration]_1 + \dots + [duration]_n)$   
 where
    - $[Dose\_w]_n = [dose]_n * [frequency]_n$
    - $[Duration]_n = [Prior\ ESA\ start\ date]_{n+1} - [prior\ ESA\ start\ date]_n^*$   
 or  
 $[Randomization\ date] - [prior\ ESA\ start\ date]_n^*$   
 when  $n^{th}$  record is the last prior ESA dose

\*Using "[end date] – [start date] + 1" may be inappropriate because the start date may be identical with the end date in case the dose frequency is once daily or twice daily, etc.

Note: Frequency is defined as follows:

If subject receives prior ESA x times per week → frequency = x

If subject receives prior ESA every x weeks → frequency = 1/x

If subject receives prior ESA x times per month → frequency = x \* 7 / 30.4375

If subject receives prior ESA x times per day → frequency = x \* 7/duration

once daily (QD) = 1 time per day, twice daily (BID) = 2 times per day, etc...

- Prior ESA dose during the period of 12 weeks prior to randomization will be used for calculation.
- To obtain this, some records may be converted for calculation because some dosing records may include both before and after the period or may not include the period.
  - If a start date of dosing is before 12 weeks prior to randomization (i.e., study day < -84), the start date will be replaced to the date of study day = -84 for the calculation.
  - This conversion makes the records before 12 weeks prior to randomization ignorable because the records will lose their information and weighting of duration before the period.

Demographics and Baseline Characteristics						
Illustration of Standardized Mean Prior ESA calculation (ex: epoetin IV)						
Record#	Visit	Start Date	Dose (IU)	Frequency. [unit]	Duration (days)	Dose_w (IU / week)
1	Screening	06Feb2017	750	Once daily	2	$750 * 7/2 = 2625$
2	Screening	08Feb2017	750	Once daily	2	$750 * 7/2 = 2625$
3	Screening	10Feb2017	1500	Once daily	3	$1500 * 7/3 = 3500$
4	Screening	13Feb2017	750	3 [times/week]	9	$750 * 3 = 2250$
-	Day 1	22Feb2017 [Randomization Date]				Weighted mean (IU/week) = 2578.1
Erythropoietin Resistance Index (ERI) at Baseline						

 
Calculated as standardized mean prior ESA dose (IU/week) divided by dry weight (kg) at screening visit and then divided by the achieved Day 1 Hgb (g/dL).
 
						

Exposure									
Blinded Dose Level									

 
Blinded dose level of each visit will be linked with prescribed dose according to the protocol:
 
									
Dose level	0	1	2	3	4	5	6	7	8
Treatment	Prescribed Dose								
Daprodustat / Placebo	0 mg	1 mg	2 mg	4 mg	6 mg	8 mg	12 mg	18 mg	24 mg
Darbeoetin Alfa / Placebo	0 µg	10 µg	15 µg	20 µg	30 µg	40 µg	60 µg	NA	NA

 
In darbeoetin alfa / placebo treatment, prescribed dose will be associated with exposure records. Two records of exposure within a certain visit form have a certain blinded dose level.
 
									
Prescribed Dose and Actual Dose									

 
Prescribed dose will be derived from blinded dose level captured in eCRF.
 
Actual dose will be derived from container number(s) captured in eCRF. Note that unscheduled (additional) bottles will not be taken into account. In principle, actual dose will be the same as prescribed dose except for a case in which inconsistency between a prescribed dose and actual bottle(s) occurs. If such an inconsistency occurs, it may not be possible to determine what dose was actually taken. In these cases, the actual dose may be changed from the prescribed dose to a more plausible value based on the available information (e.g., IRT data).
 
									
Extent of Exposure of Daprodustat									

 
Subjects who were randomized but did not report a treatment start date will be categorized as having zero days of exposure.
 
Time on study treatment will be calculated based on the following formula: Time on study treatment (days) = [Study Treatment Stop date] – [Study Treatment Start date] + 1 day The time on study treatment does not exclude dose interruptions.
 
									

Exposure

 
• Cumulative dose will be based on the formula using actual dose: Cumulative Dose = Sum of ([Exposure Duration] x [Actual Dose]) at Each Visit where Exposure duration = [Treatment Stop date] – [Treatment Start date] +1 day
 
• Subject daily dose (= Cumulative Dose / Time on study treatment) is calculated for each subject using actual dose and the summary statistics are calculated based on the subject average daily dose.
 
• Distribution of the dose level Dose level will be classified into 9 categories; 0 mg (i.e. treatment interruption), 1 mg, 2 mg, 4 mg, 6 mg, 8 mg, 12 mg, 18 mg, 24 mg according to actual dose.
 

Extent of Exposure of Darbepoetin Alfa

 
• Subjects who were randomized but did not report a treatment start date will be categorized as having zero days of exposure.
 
• Time on study treatment will be calculated based on the following formula: Time on study treatment (days) = [Study Treatment Stop date] – [Study Treatment Start date] + 1 day The time on study treatment does not exclude dose interruptions.
 
• Cumulative dose will be based on the formula using actual dose: Cumulative Dose = Sum of Actual Dose at Each Visit
 
• Subject weekly dose (= Cumulative Dose / Time on study treatment) is calculated for each subject using actual dose and the summary statistics are calculated based on the subject average weekly dose.
 
• Distribution of the dose level Dose will be classified into 7 categories; 0 µg (i.e. treatment interruption), 10 µg, 15 µg, 20 µg, 30 µg, 40 µg, 60 µg according to actual dose.
 

Treatment Compliance of Daprodustat

 
• Treatment compliance will be calculated for daprodustat as follows: 
 
○ Compliance (%) = [(Total # of tablets actual taken) / (Total # of tablets planned taken)] * 100 where Total # of tablets actual taken = Sum of (Numbers of Tablets Taken at Each Visit) Total # of tablets planned taken = Sum of [(Treatment Stop Date – Treatment Start Date + 1 day) x Planned # of tablet / day in Each Visit]
 
○ Daprodustat compliance will also be categorized based on calculated compliance: Calculated compliance < 80% → Under Compliant Calculated compliance ≥ 80% and ≤ 120% → Compliant Calculated compliance > 120% → Over Compliant
 
 
 
 
Where a container number is available, planned # of tablet/day is defined as follows according to the protocol:
 
 
○ 0 mg → 1 tablet/day (i.e., subjects takes placebo tablets)
 
○ 1 mg → 1 tablet/day
 
○ 2 mg → 1 tablet/day
 
○ 4 mg → 1 tablet/day
 
○ 6 mg → 1 tablet/day
 
○ 8 mg → 2 tablets/day
 
○ 12 mg → 2 tablets/day
 
○ 18 mg → 3 tablets/day
 
○ 24 mg → 4 tablets/day
 
 
where dose record is derived from prescribed dose.
 
Where a container number is not available (i.e., bottles not delivered to a subject), planned # of tablet/day will be 0 so that the treatment compliance will not be calculated.

Exposure
Where unscheduled (additional) bottles are being captured, the total # of tablets actual taken will be slotted to the corresponding scheduled visit.
Treatment Compliance of Darbepoetin Alfa

 
• Treatment compliance of darbepoetin alfa will be based on dosing records (weekly doses are captured) and categorized as Under Compliant, Compliant, and Over Compliant, and will be defined as follows:             
 
○ Calculated compliance < 80% → Under Compliant
 
○ Calculated compliance ≥ 80% and ≤ 120% → Compliant
 
○ Calculated compliance > 120% → Over Compliant
 
 
 
• Calculated compliance will just be carried to derive compliance category, not provided for any displays. It will be carried using the following formula:             
 
○ Calculated compliance (%) = [(Total # of dosing records with container number) / (Total # of planned dosing)] * 100
 
             where              Total # of planned dosing = [Time on study treatment (days)] / 7              where Time on study treatment (days) = Treatment Stop Date – Treatment Start date + 1           
 
 
When a container number is available in a visit, subjects will receive an injection in the visit (i.e., dosing records may be available even when subjects don't receive injections).
 
 
• For compliance up to Week 4, following formulae will be used:             
 
Total # of actual dosing up to Week 4 = Sum of (Number of dosing records with container number before Week 4 visit)
 
Total # of planned dosing up to Week 4 = [Time on study treatment (days) up to Week 4] / 7
 
• Time on study treatment (days) up to Week 4                = [Week 4 Dosing Date] – [Treatment Start date] + 1 day                If Week 4 dosing date is missing (i.e., withdrawal before Week 4), treatment stop date will be used instead.
 
 
 
• For compliance during the primary efficacy evaluation period, following formulae will be used:             
 
Total # of actual dosing during the EP = Sum of (Number of dosing records with container number on and after Week 40 visit).
 
Total # of planned dosing during the EP = [Time on study treatment (days) during the EP] / 7
 
• Time on study treatment (days) during the EP                = [Treatment Stop Date] – [Week 40 Dosing Date] + 1 day                If Week 40 dosing date is missing (i.e., withdrawal before Week 40), the compliance will not be calculated.
 
 
 

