Simulation results using the longitudinal model showed that drug response to daprodustat regarding Hg greatly varied among subjects, indicating that the dose range from 1 to 24 mg may be necessary to achieve and maintain target Hgb. Accordingly, a total of 8 dose levels (1, 2, 4, 6, 8, 12, 18, and 24 mg) were selected as the maintenance doses, with 4 mg intended for subjects with a standard drug response. The dose adjustment algorithm was defined so that target Hgb (10.0-12.0 g/dL) set for the present study according to the Guidelines for Renal Anemia [The Japanese Society for Dialysis Therapy, 2016] can be maintained. Given a difference of 1.0 g/dL between the the upper limit of Hgb target range (12.0 g/dL) and ESA dose interruption criteria value (13.0 g/dL), the dose of daprodustat will be reduced to the one step lower dose level when Hgb increases into the range of 12.0−13.0 g/dL. Since it is well known that an Hgb increase of 0.5 g/dL or less per week is appropriate to prevent adverse reactions, the dose level will be reduced by one step when Hgb increases by more than 2 g/dL over 4 weeks [KDIGO, 2012]. For subjects whose anemia needs to be corrected (≥7.5 g/dL and <10.0 g/dL),

the dose level will be maintained while the Hgb increase per 4 weeks is 0.5-2 g/dL, and the dose level will be increased by one step when the Hgb increase per 4 weeks is less than 0.5 g/dL.

Starting dose and dose adjustments of control (darbepoetin alfa)

The starting doses and dose adjustment algorithm for darbepoetin alfa are described in Section 6.4. The starting doses of darbepoetin alfa for subjects currently treated with epoetin were selected based on the prescribing information in Japan. For subjects on epoetin beta pegol, given that no recommended starting doses of darbepoetin alfa when switched from epoetin beta pegol approved in Japan is available, switchig will be performed in the epoetin beta pegol-to-darbepoetin alfa dose ratio of 5:6 at the middle dose level of darbepoetin alfa according to the overseas prescribing information [MIRCERA. Product information in Europe, 2012]. At the other dose levels, dose conversion will be performed within the approved dose levels and in a dose ratio close to 5:6.

The dose adjustment algorithm for darbepoetin alfa was determined based on the product information and previous Japanese clinical studies in accordance with the Guideline for Renal Anemia in Chronic Kidney Disease [Japanese Association for Dialysis Therapy, 2016].

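### The SAP's prior-ESA factors rank epoetin beta pegol below darbepoetin per µg (0.83) while the protocol's 5:6 ratio ranks it above (1.20); reconcile the pegol factor before unblinding

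*SAP*

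**What the plan says.** SAP 15.6.2 (Prior ESA Dose at Baseline) has each patient's previous ESA dose "standardized to obtain a continuous single unit prior ESA dose in terms of epoetin IV (IU/week"). For the two long-acting agents the factors are "Standardized mean prior ESA dose (IU/week) = 250\*darbepoetin alfa dose" and "Standardized mean prior ESA dose (IU/week) = 208\*epoetin beta pegol dose", both per µg per week and both regardless of IV or SC route. The stated basis is "The standardization will be carried with the following formula based on literature review". Within that list only the epoetin SC factor (161/113) carries a reference. SAP section 14 contains no entry tied to 250 or 208, and SAP Table 1 records no departure from the protocol's conversion.

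Protocol 4.5 sets the switch from pegol at an "epoetin beta pegol-to-darbepoetin alfa dose ratio of 5:6 at the middle dose level"; at the other levels, "dose conversion will be performed within the approved dose levels and in a dose ratio close to 5:6". Protocol Table 7 (6.4.2.1) puts this into practice: pegol ≤50, 75, 100, 150 and ≥200 µg every 4 weeks are matched to darbepoetin 15, 20, 30, 40 and 60 µg weekly.

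The standardised dose is then used in SAP 5.4.2, with prior-dose subgroups cut at 4,500 and 6,000 IU/week, and in ERI (dose divided by dry weight and by Day 1 Hgb), which is split by tertile.

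**The concern.** Two conversions of the same pair of drugs point in opposite directions. In the protocol a µg of pegol counts for more than a µg of darbepoetin; in the SAP it counts for less. Nothing in the SAP explains the reversal.

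At stake is the meaning of the prior-dose and ERI displays. Protocol 4.5 names prior ESA dose as a major factor affecting Hgb. The SAP's revision history says that the summaries by prior ESA dose, type and ERI were added to help review the switch from ESA to daprodustat. If pegol doses sit too low on the common scale, pegol users collect in the lower strata. A difference between dose strata could then be a difference between ESA types.

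**Working it through.** **Inputs.** SAP 15.6.2: 250 and 208 IU per µg. Protocol 4.5: 5:6. Protocol Table 7: the pegol and darbepoetin rows. SAP 5.4.2: cut points 4,500 and 6,000. Protocol inclusion criterion 4: pegol up to 250 µg per 4 weeks. Weekly pegol = four-weekly dose / 4, as in the SAP's frequency rule.

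**The SAP's own figures.** Its worked example reproduces: (2,625 x 2 + 2,625 x 2 + 3,500 x 3 + 2,250 x 9)/16 = 41,250/16 = 2,578.1 IU/week. It uses epoetin IV only, so it tests neither factor. The SAP does not show how 208 arose. Applying 5:6 as the protocol writes it gives 250 x 6/5 = 300; applying it the other way gives 250 x 5/6 = 208.3.

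**Implied ratio.** SAP: 208/250 = 0.832. Protocol 4.5: 6/5 = 1.20.

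**Named Table 7 doses.** Table 7 ratio = weekly darbepoetin / weekly pegol. Gap = larger / smaller standardised dose within the pair. Stratum in brackets.

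| Pegol µg per 4 weeks | Pegol µg/week | Darbepoetin µg/week | Table 7 ratio | Darbepoetin x 250 | Pegol x 208 | Gap | Pegol x 300 | Gap |
|---|---|---|---|---|---|---|---|---|
| 50 | 12.5 | 15 | 1.20 | 3,750 (low) | 2,600 (low) | 1.44 | 3,750 (low) | 1.00 |
| 75 | 18.75 | 20 | 1.07 | 5,000 (middle) | 3,900 (low) | 1.28 | 5,625 (middle) | 1.125 |
| 100 | 25 | 30 | 1.20 | 7,500 (top) | 5,200 (middle) | 1.44 | 7,500 (top) | 1.00 |
| 150 | 37.5 | 40 | 1.07 | 10,000 (top) | 7,800 (top) | 1.28 | 11,250 (top) | 1.125 |
| 200 | 50 | 60 | 1.20 | 15,000 (top) | 10,400 (top) | 1.44 | 15,000 (top) | 1.00 |

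At 208, two of the five pairs are split across strata (75 and 100 µg). At 300, none is. For equal weight and Hgb, ERI carries the same gaps.

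**Open-ended rows.** At 25 µg the ratio is 15/6.25 = 2.4; at the 250 µg cap it is 60/62.5 = 0.96. A ratio of 0.832 in the ≥200 row would need 60/0.832 = 72.1 µg/week, or about 288 µg per 4 weeks, above the cap. At the nominal four-week interval, then, no eligible dose that Table 7 maps gives 0.83.

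**Monthly coding.** For records under "If subject receives prior ESA x times per month" the SAP uses x times 7/30.4375, so 75 µg is 17.25 and 100 µg is 23.0 µg/week. At 208 these are 3,588 and 4,784 (low, middle); at 300 they are 5,175 and 6,899 (middle, top). The strata match those in the table in both cases.

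**The case against.** **The basis may be the literature.** Table 7 is a switching table rounded to available dose levels, and an analysis scale may rest on other evidence. That stands: the documents do not show which values the literature supports. But no reference is given for 208 or 250, and the SAP does not say that it departs from protocol 4.5, so a reader cannot tell a deliberate choice from an error.

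**The 1.07-1.20 range is not universal.** It holds at the named doses; the open-ended rows run from 2.4 down to 0.96. Table 7 also allows ±1 week on the pegol interval. A patient held at three weeks throughout would have three quarters of the ratio (1.20 x 0.75 = 0.90; 1.07 x 0.75 = 0.80). This is best read as a timing tolerance; the ratio the protocol states remains 5:6.

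**A reader might infer that 250 is wrong too.** Table 7's epoetin rows give 3,000/15 = 6,000/30 = 200 and 4,500/20 = 9,000/40 = 225 IU per µg of darbepoetin. But those rows name no route, and protocol 4.5 says only that "The starting doses of darbepoetin alfa for subjects currently treated with epoetin were selected based on the prescribing information in Japan". The SAP multiplies SC epoetin by 161/113 = 1.425, so for SC users the same rows give 285 to 321. Across routes the range is 200 to 321, and 250 lies inside it. The pegol range is likewise wide: 240 (IV) to 342 (SC). The epoetin rows therefore cannot fix the absolute factors. The comparison of pegol with darbepoetin is free of this problem, because the SAP applies both factors to either route.

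**The effect is small and partly visible.** Prior ESA type is its own subgroup, the prior-ESA summary is also given by type, subgroups are optional, and SAP 5.4.2 lets thresholds be added. All true, and the reason for the low severity. Added thresholds would not repair the scale.

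**Conclusion.** The pegol factor, used beside 250 for darbepoetin, contradicts protocol 4.5 in direction and size: 0.83 against 1.20. At the named Table 7 doses pegol is understated relative to darbepoetin by 1.28- to 1.44-fold, and two of five dose levels fall one stratum too low against their darbepoetin pair.

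Severity is low. The primary MMRM and the principal secondary logistic model adjust for baseline Hgb and use neither prior dose nor ERI, and the factors are the same in both arms. What is touched is the baseline summary, the optional subgroups (called exploratory for the principal secondary endpoint), the secondary displays by prior dose and ERI, and the exploratory scatter plots.

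The match of 208 with 250 x 5/6 tempts one to say that the ratio was inverted. It suggests this but does not establish it. Nor is 250 shown to be wrong, and no view is taken on the Table 7 dosing itself.

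The strata results assume stable doses at the nominal four-week interval; the SAP takes a duration-weighted mean over 12 weeks, so patients whose dose changed may land elsewhere. The share of pegol users, and hence the shift in ERI tertiles, is not known from the documents.

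**What to change.** Before unblinding, and for the analysis scale only, reconcile the pegol factor in SAP 15.6.2 with protocol 4.5 and state its basis. One way is to keep 250 for darbepoetin and use 250 x 6/5 = 300 for pegol. The largest pegol-darbepoetin gap at the named Table 7 doses then falls to 1.125-fold, with no such pair split across strata. Recompute prior ESA dose, ERI and the ERI tertiles afterwards. If 208 is kept, cite its source and explain why it departs from protocol 4.5; a reference for 250 should be added in either case.

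Cost: one constant, one sentence of justification with references, and the matching line in the derivation program.
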